In our unit, infants ≤ 32 weeks GA with RDS being treated with NIV receive *caffeine* shortly after starting NIV as recommended/reported in the literature^{7,74}. Enrolled infants will receive the 1st dose of caffeine prior to study intervention as standard clinical care in this study. This will prevent confounding of assessment of efficacy of study intervention both within and between subjects by caffeine effect. Caffeine therapy will consist of an intravenous loading dose of 20 mg/kg caffeine citrate/kg body weight followed by a daily maintenance dose of 5 mg/kg; duration of treatment will be determined by the clinical team.

Recommended criteria for intubation will be same as defined under Exit criteria (Section 3.6.5). If in an enrolled infant respiratory distress progresses and criteria for intubation are met prior to the institution of nebulized surfactant, the infant will exit the study and rescue therapy will be instituted immediately. *Recommended criteria for adjustments to ventilator settings* on conventional and high frequency ventilation include maintaining PaO₂ 50 to 70 mmHg, or oxygen saturation 90% - 95%, and PaCO₂ <65 mmHg.

Infants who are enrolled in the study and subsequently require intubation may receive *intratracheally instilled surfactant* at the discretion of the clinical team. It is not necessary to wait 6 hours from last dose of AS to administer the first dose of intratracheal surfactant if other clinical criteria are met⁷⁵. *Criteria for subsequent clinical intratracheal surfactant doses* (drawn from a clinical stock of Survanta) will include need for MV with FiO₂ >0.30 and mean airway pressure >7 cm H₂O for ≥ 20 min at ≥ 6 hours from last dose^{69,76}.

It will be recommended that extubation be attempted within 24 hours after the infant meets all of the following criteria: PaCO₂ <65 mm Hg, pH >7.20, SpO₂ 90-95% with an FiO₂ < 0.50, mean airway pressure <10 cm of water, ventilator rate < 20 breaths per minute, an amplitude of less than twice the mean airway pressure if high-frequency ventilation is being used, and hemodynamic stability⁷⁵.

All PT neonates with respiratory distress requiring NIV receive a *chest radiograph* (CXR) as standard clinical care; a CXR is not mandatory prior to enrollment for this study. *Echocardiography* and *cranial sonography*, will be performed at the discretion of the clinical team based on infants GA and clinical status.

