The Phase I/II Clinical Trial under this protocol does not have a placebo group; all randomized subjects receive active treatment. Preterm infants 24 0/7 - 36 6/7 weeks gestation that were admitted to the Hutzel Women's hospital NICU during the enrollment period (Dec 10, 2014 to Aug 31, 2017) will serve as historical controls to be able to compare intubation rates in infants enrolled and those not enrolled in the study. This will also allow comparison of other in-hospital outcomes, give an idea of numbers of infants available for the future Phase III clinical trial and the optimal time for administering study intervention.

1.1.6. Exit Criteria/Treatment Failure Criteria:

It will be suggested that infants be intubated and receive MV if they met 2 or more of 5 failure criteria:

- i). worsening clinical signs of respiratory distress (increasing tachypnea; expiratory grunting; intercostal, subcostal, and/or sternal recession);
- ii). apnea treated with positive pressure ventilation (PPV) by mask on 2 or more occasions in 1 hour;
- iii). FIO₂ >0.5 to maintain pulse oxygen saturations 90%-95% for >30 minutes;
- iv). pH <7.2 on 2 arterial or capillary blood gases taken >30 minutes apart; and
- v). partial pressure of CO₂ (PCO₂) of >65 mm Hg on 2 CBG/ABGs taken 30 minutes apart.

1.1.7. Primary outcome:

1.1.7.1. Safety:

Safety will be assessed by monitoring for oxygen desaturations, apnea, bradycardia/tachycardia, hypotension, air leaks, need for resuscitation, nasal trauma score, agitation, blockage of nasal prongs or NIV circuit, and cerebral oxygen saturation prior to, during and after study drug administration (Adverse Event [AE] Monitoring Form, Appendix VII [Table A8, A9]). Other safety measures that will be monitored include increased secretions requiring suctioning, coughing/gagging, surfactant reflux from nose/mouth, rainout in ventilator tubing, dislodged nasal prongs, abdominal distension, and nebulizer malfunction. It is expected that need for intubation is likely to be higher in the lower GA group strata.

1.1.7.2. Feasibility:

We define feasibility for this pilot RCT as the ability to:

- i). Safely deliver AS to PT infants with RDS without interrupting clinical care because of clogged nasal prongs or ventilator alarms related to inline nebulization. At the end of AS a Feasibility Questionnaire will be administered to bedside nurses & respiratory therapists to evaluate this (Appendix VIII).

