- ii). Secure cooperation of clinical bedside nurses and respiratory therapists in administering aerosol.
- iii). Identify and randomize a sufficient number of patients within a reasonable study period. This includes ability to identify eligible infants, obtain informed consent, and prepare and deliver aerosolized study medication in the defined time frame.

1.1.7.3. Dose Finding:

We will randomize infants to receive one of 4 fixed dosing schedules. Data collected during this Phase I/II trial will be critical in selecting the optimal dosing schedule for the definitive Phase III trial. Optimal dosing schedule will be determined by preliminary evidence of efficacy, lack of adverse effects, and tolerance by patients and bedside clinical caregivers.

1.1.7.4. Efficacy:

The primary efficacy outcome for this Phase I/II trial is the need for need for intubation and MV within 72 hours of study intervention (treatment failure). This will be compared to a historical control rate of 0.5 for need for intubation in PT infants 24-36 weeks GA undergoing NIV. Treatment failure criteria are defined *a priori* in Section 3.6.5. We chose treatment failure within 72 hours of randomization as our primary efficacy outcome as failure within that time would likely be due to RDS, whereas failure after this time would more likely be due to secondary causes like sepsis, PDA, pneumonia, NEC, IVH, or apnea of prematurity.

1.1.8. Secondary Efficacy Outcomes:

1. CBG/ABG, pulse oximetry, vital signs at 60±30 minutes after end of AS
2. Number of doses of surfactant – aerosolized & intratracheal
3. Respiratory support at 24, 48 & 72 hours, 7 days (D7), D14, D28, 36 weeks corrected GA and Discharge.
4. Pneumothorax, pneumomediastinum or other air leak
5. Changes in cerebral oxygenation as evaluated by NIRS
6. Changes in surfactant activity in gastric aspirates
7. Cumulative duration of NIV and invasive ventilation on D3, D7, D14, D28, 36 weeks CGA and discharge
8. Duration of supplemental oxygen, intensive care, hospital stay
9. Age at start of feeds, feeding progression, age at full enteral feeds
10. Need for blood transfusions
11. Growth parameters at 7 days, 28 days, 36 weeks corrected GA and discharge
12. Morbidities associated with prematurity: PDA, IVH (Grade III-IV), NEC, periventricular leukomalacia, ventriculomegaly, ROP (stage>3 or requiring treatment), and BPD. Two definitions of BPD will be used:

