In this safety, feasibility and dose finding Phase II trial, 30 infants will be assigned to each of the 4 dose schedules^{4,88}. The aim of phase II trials is to explore different doses, evaluate safety & tolerability, and obtain early indication of efficacy⁸⁸. The dose-safety relationship is more important than the dose-efficacy one as efficacy is irrelevant if the dose is unsafe⁸⁹. Phase II trials are generally inadequate with respect to size, outcome, precision, and control of bias to provide formal proof of efficacy^{3,90}. Rather these trials provide baseline data, potential primary outcome and effect size justifying the larger, longer, and more expensive Phase III trial. *Recognizing that our Phase II trial is not powered for efficacy, sample size calculations based on precision of the estimate of the primary outcome & the null hypothesis and error rate are presented below.*

Sample Size Based on Precision for the Primary Efficacy Outcome:

The efficacy goal of Phase II studies is typically to estimate a clinical endpoint with a specified precision. The primary efficacy outcome in this study is the need for intubation & MV within 72 hours of AS. Using the normal approximation to the binomial as described by Piantadosi⁸⁸ ($w = Z_{\alpha} \times \sqrt{p(1 - p)/n}$; or more simply $n=1/w^2$ for estimated proportions (p) ranging from 0.2 to 0.8, where Z_{α} is the quantile from the normal distribution corresponding to the two-sided probability, n =sample size, w =width of the 95% confidence interval [CI] or precision), a sample size of 30 per dosing schedule group will allow evaluation of a failure rate of 0.25 - 0.4 with 95% CI of ± 0.15 to ± 0.17 (15 to 17% precision) (Table 12). The precision of this estimate is increased if we collapse the dilution groups corresponding to dose of 100 mg/kg & 200 mg/kg (<12%) or consider our entire sample of 120 subjects all of whom receive the study intervention (<9%).

Table 12: Sample Size & Precision for various proportions of primary efficacy outcome:

Sample Size	Rate	Precision for Estimating Outcome		
		95% CI		Precision
		Lower	Upper	
30 (for each dosing Schedule i.e. I, II, III, IV)	0.25	0.13	0.43	$\pm 15\%$
	0.3	0.17	0.48	$\pm 15\%$
	0.35	0.21	0.53	$\pm 16\%$
	0.40	0.25	0.58	$\pm 17\%$
60 (for each dose group 100/kg vs. 200 /kg)	0.25	0.16	0.37	$\pm 11\%$
	0.3	0.2	0.45	$\pm 12\%$
	0.35	0.24	0.48	$\pm 12\%$
	0.40	0.29	0.53	$\pm 12\%$
120 (for the whole group)	0.25	0.18	0.33	$\pm 8\%$
	0.3	0.23	0.39	$\pm 8\%$

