Data will be analyzed according to the intention-to-treat principle using SAS and PASW (IBM Inc.). We will report descriptive statistics for demographic, clinical and respiratory support data at baseline and over time for the entire sample and for the 4 dosing schedule groups (Appendix IX [Table M1, M2]). In addition, three subgroup analyses are planned – according to dose regardless of dilution (100 vs. 200 mg/kg), GA strata, nebulizer device using logistic regression incorporating an additional treatment-by-subgroup interaction term.

Analysis plan to address Aim #1 – Safety and Feasibility Assessment: Safety will be assessed by quantifying and comparing the AEs and their severity for the total sample and across the dosage/dilution groups and two types of nebulizers. Indicators include cardiorespiratory responses, blockage of NIV circuit and cerebral oxygen saturation (Appendix IX [Table M5]). Descriptive statistics (mean, standard deviation, proportion, inter-quarter range [IQR]) will be used to quantify these indicators; *confidence intervals will be preferred to hypothesis testing* as considerable imprecision is expected arising from low frequencies of these AEs³. ANOVA or *t*-test (continuous measures) and χ^2 test (categorical variables) will be used for comparative analyses though we may not find statistically significant differences. Paired *t*-test will be used to compare heart rate, respiratory rate, blood pressure, SpO₂, PCO₂, cerebral oxygenation (RCO₂, cFTOE), ACoRN score and nasal exam score before and after AS. These parameters will also be compared between infants who get intubated within 72 hours of study intervention and those who do not; and before and after intubation within subjects that get intubated. Feasibility will be assessed by quantifying and comparing the percentage of infants who tolerate the treatment procedure and responses of the clinical nurses and respiratory therapists on the feasibility questionnaire (Appendix IX [Table M6]). Because of the high inherent variability of these factors and small effect sizes, we do not expect to show significant differences between groups given our sample size. However this information will be useful in making the final decision to proceed with a Phase III RCT.

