Analysis plan to address Aim #2: - Determination of Optimal Dilution and Dosage of AS: The optimum dose is one that produces low toxicity while nearly maximizing the biological response⁸⁹. The optimal dosage will be determined by comparing levels of adverse responses, feasibility items and primary and secondary efficacy treatment outcomes (rates of intubation, diagnosis of PDA, need for blood transfusions, postnatal growth, duration of respiratory support, length of hospital stay, and incidence of complications of prematurity including IVH, sepsis, pneumonia, BPD, NEC, ROP, and death) across the four dosing schedules (Appendix IX, Mock Tables). The optimal dosage/dilution will be the one with the minimum level of adverse responses and highest clinical treatment outcomes.

Analysis plan to address Aim #3 - Short-term efficacy of AS: The primary outcome variable for short-term efficacy is the need for intubation & MV within 72 hours of AS. We will estimate the unconditional probability of benefit for the four dosing schedule groups (I, II, III, IV), the 2 dose groups (100 vs. 200 mg/kg) and the entire study cohort of 120 subjects. We will also compare with reported rates of intubation in historical controls (50%). A special χ^2 test to compare sample proportion with population proportion will be conducted to test the study hypothesis that AS is efficacious. In the comparison analysis, different dosages/dilutions will also be considered as weight using the “optimal” dosage/dilution obtained from Aim #2 as reference. A significantly lower rate of intubation in infants treated with AS in this study as compared to the reported rate of ~0.5 at $p < 0.05$ level (two-sided) will be used as evidence supporting the efficacy of AS. However, it is likely we may not

have power to achieve statistically significant results. Nevertheless these preliminary efficacy data will be crucial in determining outcome measures and effect size for the definitive placebo-controlled Phase III trial.

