2. Performing a survival curve analysis to present timing of intubation in infants who were intubated
3. Control for mode of ventilation at baseline and exploring a GA cutoff at which this intervention may be most beneficial.
4. Detailed caffeine data in relation to AS to be provided
5. DMC requested data for intubation rates in the three GA strata outside this clinical trial setting (as reported in the literature and at Hutzel Women's Hospital by initiating an observational study) as there is no placebo group in this analysis
6. Handling of infants that exited study prior to study intervention
 - a. DMC recommended performing a dual level analysis
 - i. The primary “intent to treat analysis” should include all enrolled subjects.
 - ii. A secondary “experimental analysis” should also be presented that only includes subjects that received study intervention.

REFERENCES:

1. International conference on harmonisation: General Considerations for Clinical Trials. *Fed Regist.* 1997;62(242):66113.
2. Piantadosi S. Clinical trials as experimental designs. In: Balding DJ, Cressie NAC, Fisher NI, et al., eds. *Clinical Trials: A Methodologic Perspective*. 2nd ed. New Jersey: John Wiley & Sons; 2005:127-165.
3. International conference on harmonisation; guidance on statistical principles for clinical trials; availability--FDA. Notice. *Fed Regist.* 1998;63(179):49583-49598.
4. Food, Drug Administration HHS. International Conference on Harmonisation; choice of control group and related issues in clinical trials; availability. Notice. *Fed Regist.* 2001;66(93):24390-24391.

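### The primary efficacy endpoint starts its 72-hour clock at different points, so infants who exit before aerosolized surfactant stay in the ITT set with no defined outcome

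*Combined protocol and SAP*

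**What the plan says.** **Time origin.** Section 1.1.7.4 (Efficacy) gives the primary efficacy outcome as the need for "intubation and MV within 72 hours of study intervention (treatment failure". Its rationale, in the same paragraph, reads "We chose treatment failure within 72 hours of randomization as our primary efficacy outcome". Section 1.1.10 (Sample Size) has "The primary efficacy outcome in this study is the need for intubation & MV within 72 hours of AS", and the Aim #3 analysis plan in section 1.1.12 has "The primary outcome variable for short-term efficacy is the need for intubation & MV within 72 hours of AS". No section says whether the AS clock starts at the beginning or the end of nebulization, or at the first or second dose. Section 1.1.4.4 (d, e) allows a second dose 4 hours after the first and expects nebulization of up to 4-5 hours in the largest infants.

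**Infants who never receive AS.** Every enrolled infant gets a randomized assignment (1.1.4.1, 1.1.4.7). Section 1.1.4.9 says that if "criteria for intubation are met prior to the institution of nebulized surfactant, the infant will exit the study". The criteria are those of section 1.1.6, headed "Exit Criteria/Treatment Failure Criteria".

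**Analysis set.** Section 1.1.12 states "Data will be analyzed according to the intention-to-treat principle". Item 6 of the DMC recommendations there, "Handling of infants that exited study prior to study intervention", asks for a primary ITT analysis of all enrolled subjects and a secondary analysis of those who received the intervention.

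**Premise elsewhere.** Sections 1.1.5 and 1.1.10 are written as if every randomized infant is treated. Section 1.1.10 also adds 20 places for screen failures without defining the term.

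**The concern.** The plan foresees a group of infants who are randomized, meet intubation criteria before AS and leave the study. It settles that they belong in the primary denominator. It does not settle what they contribute to the numerator, and the conflict over time origin is what leaves this open.

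At stake is the observed failure rate. Section 1.1.12 tests it against a fixed 0.5, treats p < 0.05 as evidence of efficacy, and uses it for the Phase III effect size. Leaving pre-AS intubations out of the failures, by exclusion or by default, moves that rate in one direction only, in favour of AS. Research staff know the assigned groups, so a scoring rule chosen after the data are in could also follow the result.

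**Working it through.** **1. The plan's own figure.** Inputs from section 1.1.10 and Table 13: n = 30, rate 0.25 against 0.5, two-sided 0.05. Arcsine approximation: h = 2·asin(√0.5) − 2·asin(√0.25) = 0.5236; h·√30 − 1.960 = 0.908; Φ(0.908) = 81.8%, exactly as stated. The normal approximation gives 81.6%. The plan's test rejects at 9 or fewer failures, with exact power 80.3%. The power arithmetic is sound.

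**2. An infant intubated and ventilated after randomization but before AS, under each wording.**

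| Place | Clock starts at | Status of this infant |
|---|---|---|
| 1.1.7.4, definition | study intervention | no time zero |
| 1.1.7.4, rationale | randomization | failure |
| 1.1.10 | AS | no time zero |
| 1.1.12, Aim #3 | AS | no time zero |
| 1.1.12, ITT and DMC item 6 | not stated | in the denominator, score not stated |

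**3. Treated infants.** AS is due within 8 hours of starting NIV (1.1.4.2), and randomization follows the start of NIV (1.1.4.1). If the AS clock starts with the first dose, the two windows therefore end at most 8 hours apart. If it starts at the end of a second dose, the gap could reach about 8 + 5 + 4 + 5 = 22 hours, taking 5 hours per nebulization and the 4-hour interval from the end of the first dose. The documents do not say which applies.

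**4. Shift in the rate.** Assumptions not in the documents: k exits per schedule of 30, all intubated and ventilated, and a failure rate of 0.25 among the treated.

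- Exits as failures: [k + 0.25(30 − k)]/30
- Exits excluded: 0.25, on 30 − k infants
- Exits as non-failures: 0.25(30 − k)/30

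| k | Failures | Excluded | Non-failures |
|---|---|---|---|
| 1 | 8.25/30 = 0.275 | 0.25 | 7.25/30 = 0.242 |
| 2 | 9/30 = 0.300 | 0.25 | 7/30 = 0.233 |
| 3 | 9.75/30 = 0.325 | 0.25 | 6.75/30 = 0.225 |

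Failure and exclusion differ by 0.75k/30 = 0.025, 0.050, 0.075. The non-failure column is the extreme case.

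If the planned 0.25 already counts exits as failures, the excluded rate is (7.5 − k)/(30 − k) = 0.224, 0.196, 0.167 and the non-failure rate is 0.25 − k/30 = 0.217, 0.183, 0.150. The direction is the same.

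**5. Effect on a test result.** With z = (0.5 − x/n)/√(0.25/n):

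- 9/30: z = 2.19, p = 0.028
- 10/30: z = 1.83, p = 0.068

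Illustration with 2 exits and 8 failures among 28 treated: 10/30 gives p = 0.068; 8/28 gives z = 2.27, p = 0.023; 8/30 gives z = 2.56, p = 0.011.

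**6. Power, for completeness.** Under the step 4 assumptions, exact power at k = 1, 2, 3 is 71%, 60%, 47% with exits as failures and 83%, 75%, 79% with exits excluded. The second series is uneven because the critical count is a whole number.

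**The case against.** The strongest reply is that the documents already indicate the answer. Section 1.1.4.9 makes the intubation criteria the same as the exit criteria, section 1.1.6 names these as treatment failure criteria, and the DMC item puts such infants in the primary analysis. On that reading one clarifying sentence is enough. This largely stands as to what the answer should be. It does not supply the rule: three of the four statements of the endpoint start at treatment, where the infant cannot be scored.

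Other limits also stand.

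- The number of exits is unknown. Infants needing immediate intubation are excluded (1.1.3) and AS is due within 8 hours of starting NIV, so it may be small.
- Section 1.1.10 says the trial is not powered for efficacy, and if the planned 0.25 already includes exits, scoring them as failures costs no power. The shift in the rate matters more than the power figures.
- Section 1.1.10 words the 0.5 as intubation following NIV, which suggests that early intubations are in it, but its time origin is not given.

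A reader might infer more than the documents support:

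- *That the plan overlooks pre-AS exits.* It does not; the DMC item assigns them to an analysis set.
- *That they will be counted as successes.* No section says so.
- *That the comparison between schedules is biased.* These exits precede any AS, and clinical caregivers are meant to be blinded to dose and dilution, so imbalance would be expected to arise by chance.

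**Conclusion.** The point holds and should be fixed. The endpoint has conflicting time origins in current text, and under the dominant wording a foreseen group of infants in the primary analysis set cannot be scored. Leaving them out of the failures biases the rate tested against 0.5 downward and makes the Phase III effect size too favourable.

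On the assumed 1 to 3 exits per 30 and a treated rate of 0.25, the understatement is 2.5 to 7.5 percentage points if exits are dropped and 3.3 to 10 points (k/30) in the extreme case of non-failure scoring. One infant's scoring can carry a schedule across p = 0.05. The direction follows from the definitions; the size rests on the assumed exit count. The figures use the 30 per schedule of Tables 12 and 13. With the later enlargement of Phase II to 220, the shift in the rate is unchanged for a given share of exits, while each infant weighs less.

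**What to change.** - **Sections 1.1.7.4, 1.1.10 and 1.1.12 (Aim #3):** use one definition, namely intubation and MV within 72 hours of randomization in all randomized infants, with intubation and MV before AS scored as failure.
- **Section 1.1.4.9:** state that randomized infants who exit before AS stay in the ITT set with their 72-hour outcome recorded. This concerns outcome data only.
- **Section 1.1.10 (amended total):** define screen failures and state that these randomized infants are not among them.
- **DMC's treated-only analysis:** keep it as secondary and state its time zero, including which dose and whether the start or end of nebulization.

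The cost is wording in these sections, plus 72-hour outcome records for infants who exit before AS. The reported failure rate may be slightly less favourable. No clinical management rule changes.

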Only short binasal prongs will be used for aerosol delivery in the NIV circuit. Since the ventilator circuit for NCPAP and NIPPV is identical, only one type of neonatal nasal prongs (INCA®) will be used. For the HFNC circuit, only the neonatal Fisher & Paykel short binasal prongs will be used. Nasal cannulas will be applied with recommendations that the prong outer diameter occupy $\sim 50\%$ of the nares internal diameter to allow free egress of flow around the cannula³⁴.

d) Number of doses of Aerosolized Surfactant & Intervals between Doses:

Infants will be eligible to receive a 2nd dose of AS 4 hours after the 1st dose of AS if there is continued need for NIV with FiO₂ $\geq 25\%$ or PEEP ≥ 4 cmH₂O or HFNC rate ≥ 2 LPM.

Since most PT infants with RDS receive ≤ 2 doses of intratracheal surfactant as standard of care, we chose 2 doses of AS as being the minimum number to assess efficacy without inordinately delaying standard of care treatment with intratracheal surfactant⁵⁸. Early trials of intratracheal surfactant used dosing intervals ranging from 1 to 12 hours based on ventilator settings. Since pulmonary delivery following aerosolisation is not precisely quantified, we will administer the 2nd dose 4 hours after the 1st if the infant meets criteria.

e) Duration of nebulization:

Time to nebulize each dose will depend upon volume of diluted surfactant, type of nebulizer, and ambient humidity and temperature. It is expected that for each dose nebulization will be <1 hour for the smallest infants and $<4-5$ hours in the largest infants. This Phase II study will provide critical information regarding time for nebulization of various doses for PT babies and will be crucial in determining tolerance of intervention both by the patient and clinical bedside caregivers. This will be one factor in selecting the optimal dose and dilution of AS for the definitive Phase III trial.

1.1.4.5. Gestational Age Group Strata:

Enrolled infants will be stratified by three GA strata (24^{0/7}-28^{6/7}; 29^{0/7} - 32^{6/7}, 33^{0/7} - 36^{6/7}) because need for intubation and MV has been reported to be higher in more immature infants along with higher co-morbidities of prematurity and mortality. Infants <24 weeks will be excluded as most are likely to receive intubation. ^{59,60}

1.1.4.6. Randomization Procedures: Assignment to Surfactant dosing schedule:

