 - a) Physiological definition: receipt of > 30% supplemental oxygen at 36 weeks or the need for positive-pressure support or, in the case of infants requiring < 30% oxygen, the need for any supplemental oxygen at 36 weeks after an attempt at withdrawal of oxygen⁸⁶.
 - b) Receipt of any supplemental oxygen at 36 weeks.
13. Survival to hospital discharge
14. Survival to discharge without severe morbidity, defined as any of the following: BPD, late onset sepsis, ROP, or serious brain abnormality (IVH, periventricular leukomalacia, or ventriculomegaly)

1.1.9. Monitoring for Adverse Events (AEs):

Adverse events (AEs) that will be monitored during the study and a toxicity grading scale for potentially serious and life-threatening AEs is defined in Appendix VII [Tables A8, A9]⁸⁷.

1. Plugging of nasal prongs, increased secretions requiring suctioning, occurrence of coughing/gagging, surfactant reflux from the nose/mouth, residual surfactant in nasal prongs or nebulizer chamber, rainout in ventilator tubing, dislodged prongs, abdominal distension, and agitation
2. Nebulizer malfunction – clogged, no visible mist, disconnected ventilator tubing
3. Bradycardia, tachycardia or hypotension requiring treatment during or within 6 hours after study intervention
4. Desaturations and/or apnea during or within 6 hours after study intervention
5. Need for resuscitation (positive pressure ventilation, chest compression or cardiac medications) during or within 6 hours after intervention
6. Air leak (pneumothorax, pneumomediastinum) during or within 6 hours after study intervention

7. Nasal trauma score (Appendix VII [Table A4]) before AS, at end of AS and 24 hours after end of AS
8. Death

1.1.10. Sample Size:

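### Aim #2 compares support time, hospital stay and BPD across schedules with no rule for deaths, so early death can make a schedule look better on them

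*Combined protocol and SAP*

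**What the plan says.** Section 1.1.8 (Secondary Efficacy Outcomes) lists:

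- item 2: "Number of doses of surfactant – aerosolized & intratracheal"
- item 7: "Cumulative duration of NIV and invasive ventilation on D3, D7, D14, D28, 36 weeks CGA and discharge"
- item 8: "Duration of supplemental oxygen, intensive care, hospital stay"
- item 12: morbidities including BPD, under a physiological definition and a simpler one, "Receipt of any supplemental oxygen at 36 weeks"
- item 13: "Survival to hospital discharge"
- item 14: "Survival to discharge without severe morbidity, defined as any of the following: BPD, late onset sepsis, ROP, or serious brain abnormality", where the last term covers IVH, periventricular leukomalacia and ventriculomegaly.

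Section 1.1.12, Aim #2, compares the four schedules on adverse responses, feasibility, and primary and secondary efficacy outcomes. Its bracketed list names time on respiratory support, hospital stay, BPD and death as separate entries. It does not name item 14, dose counts, NIV hours or oxygen time. The selection rule is: "The optimal dosage/dilution will be the one with the minimum level of adverse responses and highest clinical treatment outcomes". No weights or order are given.

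The later text of 1.1.12 plans means or medians for continuous secondary outcomes, compared by t-test, ANOVA or nonparametric tests, and proportions for dichotomous ones. Neither this text nor the DMC recommendations that close the section say how a death enters a duration or the BPD denominator. Section 1.1.4.4 d) allows a second aerosol dose "if there is continued need for NIV with FiO₂ $\geq 25\%$ or PEEP ≥ 4 cmH₂O or HFNC rate ≥ 2 LPM".

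**The concern.** Less support time, a shorter stay and less BPD are good news only in infants who live. An infant who dies in the first days adds a few days to each duration and can never be classed as having BPD at 36 weeks. Section 1.1.4.5 itself notes higher mortality in more immature infants, and section 1.1.10 keeps enrolment open in the lowest gestational-age stratum, so some deaths should be expected.

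If deaths fall unevenly across schedules, by chance or otherwise, the schedule with more of them gains on three of the outcomes that Aim #2 uses to choose a schedule for Phase III. A related point concerns items 2 and 7. Intubation ends NIV and closes the route to a second aerosol dose, so NIV hours or aerosol doses read on their own can fall because treatment failed.

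**Working it through.** The plan states no figure for stay, BPD, mortality or NIV hours, so there is none to reproduce. From section 1.1.10 come 30 infants per schedule, the 50% historical intubation rate and the 25% target. Every other input below is an assumption.

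**1. Hospital stay.** If k infants die on day t instead of staying L days, the mean over n infants changes by −k(L − t)/n.
- n = 30, t = 3, k = 1: (40 − 3)/30 = 1.2 days and (60 − 3)/30 = 1.9 days shorter.
- k = 2: 2 × 37/30 = 2.5 and 2 × 57/30 = 3.8 days shorter.
- Death on day 14, k = 1: 26/30 = 0.9 and 46/30 = 1.5 days shorter.
- Enlarged trial of 220, less the 20 allowed for screen failures: 200/4 = 50 per schedule, so one day-3 death gives 37/50 = 0.7 and 57/50 = 1.1 days.

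Total support time is cut short in the same way. A median would move less than a mean.

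**2. BPD.** Let b be the BPD rate in survivors and m the mortality before 36 weeks. Over all randomized infants, BPD alone is b(1 − m) and death-or-BPD is m + b(1 − m). Raise m from 0 to 20%:

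| b | BPD alone | Death-or-BPD |
|---|---|---|
| 20% | 20% → 16% | 20% → 36% |
| 40% | 40% → 32% | 40% → 52% |
| 60% | 60% → 48% | 60% → 68% |

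With survivors only in the denominator, BPD stays at b. It would fall only if the infants who died were those at higher risk of BPD. The plan does not state the denominator.

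**3. NIV time (item 7).** Mean NIV hours to D3 = (1 − p) × hours in successes + p × hours in failures.
- Assume 60 h and 12 h. At p = 50% the mean is 30 + 6 = 36 h; at p = 25% it is 45 + 3 = 48 h. Fewer failures give more NIV hours.
- Now sum NIV and invasive time, with failures on a ventilator up to 72 h. At 50% the mean is 30 + 36 = 66 h; at 25% it is 45 + 18 = 63 h. Fewer failures give less total support.
- To D7, assume 3 days of NIV in non-failures and 4 in failures. NIV alone is then 3.25 days at 25% failure and 3.5 days at 50%, so here more failures give more NIV.

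The misleading direction arises only when NIV is read alone, and not always then.

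**4. Doses (item 2).** Let f be the failure rate, q the share of non-failures given a second dose, and e the share of failures that come before dose 2. Mean aerosol doses = (1 − f)(1 + q) + f(2 − e). Raise f from 25% to 50%:
- q = 0.3, e = 0.3: 1.40 → 1.50
- q = 0.3, e = 0.6: 1.325 → 1.35
- q = 0.6, e = 0.3: 1.625 → 1.65
- q = 0.6, e = 0.6: 1.55 → 1.50

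Adding one intratracheal dose per failure, the total rises in all four cases (in the last, 1.80 → 2.00). The aerosol count alone has no fixed direction; the combined count rises with failure.

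**The case against.** The plan does not ignore death. It is item 13, an adverse event in section 1.1.9 and an entry in the Aim #2 list, and section 1.1.10 ranks the dose-safety relationship above efficacy. Item 14 already combines death with BPD. For skewed data the plan specifies medians and nonparametric tests, and one death in 30 hardly shifts a median. Infants expected to die within three days are excluded, so a day-3 death is an extreme case. The mock tables in Appendix IX, where a rule might stand, are not in the public document. The outcomes are secondary in a trial that says it is not powered for efficacy.

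Most of this stands and limits the severity. It does not remove the point. Counting death in one column leaves the support, stay and BPD columns uncorrected, and with no weights a reader cannot tell how they offset one another. Item 14 mixes in sepsis, ROP and brain injury, so it does not isolate death-or-BPD, and the Aim #2 list does not name it. If Appendix IX does hold a rule for deaths, the durations and the BPD denominator need only a cross-reference to it.

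**Conclusion.** The point holds, with modest severity. Three outcomes named for schedule selection are cut short by death, and the visible plan has no rule for this. The size rests on assumed stays and on where deaths fall: about 1.2 to 1.9 days of mean stay per day-3 death among 30 infants, less for later deaths, larger groups or medians. For BPD the effect is mechanical only if all randomized infants form the denominator.

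A reader might infer more: that treatment failure in general flatters these outcomes, and that the plan ranks schedules on NIV hours, aerosol doses and oxygen time. The documents do not support that. Nothing in them suggests that intubation shortens oxygen time or stay, or lowers BPD; only death does. Items 2 and 7 also list intratracheal doses and invasive ventilation, which rise with failure. Dose counts, NIV hours and oxygen time could enter Aim #2 only through its general reference to secondary outcomes. Nor would it be right to say that the plan never combines BPD with death, since item 14 does.

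**What to change.** In section 1.1.8 and Aim #2:

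- Report death-or-BPD at 36 weeks beside BPD alone, and state the denominator of each.
- Compare schedules on days alive and free of invasive ventilation, and days alive and free of any respiratory support, over a fixed window named in advance (for instance to D28). Death counts as 0 days, and groups are compared by ranks. Keep the raw durations as descriptive data.
- Report length of stay in survivors, beside mortality.
- Report NIV time and invasive time separately, and aerosol and intratracheal doses separately. State that fewer NIV hours or fewer aerosol doses alone are not read as benefit, because early intubation can cut both short.

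The cost is SAP wording and some derived variables. Respiratory support and outcomes to discharge are already recorded under section 1.1.4.10, so no new data are needed. The downside is that free-day outcomes are skewed and combine death with duration, so deaths and durations must be shown beside them.
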